*Mild psoriasis - psoriasis affected Body Surface Area (BSA) less than 10% and Psoriasis Area and Severity Index (PASI) between 6 and 12.
*Group 1 : 6 months secukinumab + 12 months observation
*Group 2 : 3 months placebo + 3 months secukinumab + 12 months observation
- 2) To explore whether secukinumab will prevent relapses after medication has been discontinued in subjects with mild plaque-type psoriasis.
- 3) To compare frequency of relapse between subjects who achieve a score of 0 (clear) on IGA (Investigator's Global Assessment) and subjects who do not achieve a score of 0 (clear) on IGA, within each group (Group 1 (6 months secukinumab) and Group 2 (3 months Placebo + 3 months secukinumab)).
- 4) To compare frequency of relapse between subjects who achieve a score of 0 (clear) on IGA between group 1 and group 2 (Group 1 (6 months secukinumab) and Group 2 (3 months Placebo + 3 months secukinumab)).
- 5) To evaluate the safety of secukinumab for the treatment of subjects with mild plaque-type psoriasis comparing the secukinumab-receiving mild psoriasis subjects (Group 1) and the placebo-receiving mild psoriasis subjects (Group 2) for 3 months.

12.7 * Primary Outcome(s)

Indicate which *variable(s)* will be assessed to judge the primary specific aim. Give measurement units, if applicable.

- 1) The proportion of subjects who have a reduction of 75% or more from baseline in the psoriasis area-and-severity index score (PASI 75) at week 12 (*primary endpoint*)¹
- 2) The proportion of subjects who have a reduction of 90% or more from baseline in the psoriasis area-and-severity index score (PASI 90) at week 12²
- 3) The proportion of subjects who achieve a score of 0 (clear) on a 5-point modified investigator's global assessment (IGA) at week 12³

1,2,3The 3 co-primary endpoints are subject to a step-down hierarchical closed testing procedure. (Primary objective is achieved if any null hypothesis is rejected following the order: PASI75, PASI90, IGA0).

12.8 * Secondary Outcome(s)

Indicate which *additional variable(s)* will be assessed to judge the secondary outcome(s). Give measurement units, if applicable.

- 1) The proportion of subjects who experience a psoriasis relapse at any time between week 24 and week 72. Psoriasis relapse is defined as loss of > 50% of the initial PASI improvement measured at week 24.
- 2) Severity of the relapses over the observation period.
- 3) Extent of relapse over the observation period.

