- Assessment of psoriasis, PGA, PASI with BSA, PASE, DLQI
- Adverse event assessment

Translational research: 6-mm punch skin biopsies from lesional and non-lesional skin and blood samples will be obtained at baseline and weeks 12, 24, 72, at the time of psoriasis relapses, and at early termination. Genomic profiling of psoriasis skin will be conducted with the Affymetrix Human Genome U133 Plus 2.0 Array and RT-PCR. The phenotypes of activated T cells and regulatory T cells in psoriasis patients' blood will be studied by flow cytometry. Inflammatory and cardiovascular proteins in the blood will be investigated to develop a biomarker with Proximity Extension Assay technology (OLINK®).

Structure: Double Blind, Two-arm parallel group design, Randomized 1:1.

12.10 * Data Analysis

Describe method(s) of data analysis.

For the comparison between proportions a Fisher exact test will be performed in any case. The results will be presented as contingency tables and odd ratios will be calculated. 95% Confidence Intervals will be provided. To achieve the primary objective

The comparison between times of relapse must be done using a Wilcoxon-Mann-Whitney test. A Kaplan Meier analysis will be used to establish the relapse survival curve for each group and

the log-rank test will be made. A step-down hierarchical closed testing procedure will be done considering the order: PASI75, PASI90, IGA0.

12.11 * Explain the rationale for the choice of statistical measures and the number of participants proposed for the study, including the power calculations when applicable.

1. Sample Size Calculation for Primary Objective/First outcome (3 co-primary endpoints are subject to a step-down hierarchical closed testing procedure)

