Langley et al. (2014) presented the results of two Phase 3 trials for Secukinumab: ERASURE and FIXTURE. Among others outcomes Langley reported the proportion of subjects with moderate or severe Psoriasis who achieve PASI75 (PASI score improvement over 75%) after 12 weeks of treatment in the 2 cohorts treated with Secukinumab 300 mg and the 2 Placebo cohorts with 245, 323, 246 and 324 subjects respectively. The worst scenario observed on Langley's results is: largest Placebo proportion=0.05 and smallest Secukinumab proportion=0.77. Assuming Langley's results as preliminary data, to find significant differences between groups by using a one-tail Fisher exact test with power equal to 0.95 and 99.9% of significance level, a sample size of 19 patients at each group (N=38) will be required. Considering the 5.6 % of dropout reported by Langley will be necessary to recruit 20 patients for each group (N=40). Power analysis for 3 co-primary endpoints and 19:19 patients is reported in the following table:

ENDPOINT	TREATMENT OBSERVED PROPORTION *	PLACEBO OBSERVED PROPORTION *	OBSERVED EFFECT SIZE*	SIGNIFICANCE LEVEL	POWER	DETECTABLE EFFECT SIZE
PASI 75	0.77	0.05	0.72	0.05	0.8	0.49
				0.05	0.9	0.55
				0.05	0.95	0.60
				0.01	0.8	0.42
				0.01	0.9	0.48
PASI 90	0.54	0.02	0.52	0.05	0.8	0.4
				0.05	0.9	0.47
				0.05	0.95	0.52
				0.01	0.8	0.52
				0.01	0.9	0.59
IGA0	0.24	0.01	0.23	0.05	0.8	0.37
				0.05	0.9	0.44
				0.05	0.95	0.50
				0.01	0.8	0.50
				0.01	0.9	0.56
				0.01	0.95	0.61

OR

ENDPOINT	TREATMENT OBSERVED PROPORTION *	PLACEBO OBSERVED PROPORTION *	OBSERVED EFFECT SIZE*	SIGNIFICANCE LEVEL	ESTIMATED POWER TO DETECT OBSERVED EFFECT SIZE
PASI 75	0.77	0.05	0.72	0.05	0.99
				0.01	0.99

PASI 90	0.54	0.02	0.52	0.05	0.99
				0.01	0.94
IGA 0	0.24	0.1	0.14	0.05	0.46
				0.01	0.25

* Langley et al. (2014)

2. Power Analysis for Exploratory Objectives/First outcome

Assuming the proportion of 300 mg secukinumab patients who achieve PASI 100 at week 24 as reported by Langley (0.4), the allocation ratio of subjects who achieve PASI 100 and subjects who not achieve PASI 100 for Group 1 (6 month of Secukinumab) will be 8:11. On that case a Fisher exact test to compare the proportion of patients who experience relapse with power equal to 0.80 and 95% of significance level will be able to detect significant differences only if the following relationship between proportions is observed:

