Proportion of patients from Group 1, who achieve PASI 100 at week 24 and experience relapse	Proportion of patients from Group 1, who not achieve PASI 100 at week 24 and experience relapse
0.00	0.45
0.13	0.73
0.25	0.82
0.38	0.91
0.50	1.00

Assuming the proportion of 300 mg secukinumab patients who achieve PASI 100 at week 12 as reported by Langley (0.3), the allocation ratio of subjects who achieve PASI 100 and subjects who not achieve PASI 100 for Group 1 (6 month of Secukinumab) will be 6:13. On that case a Fisher exact test to compare the proportion of patients who experience relapse with power equal to 0.80 and 95% of significance level will be able to detect significant differences only if the following relationship between proportions is observed:

Proportion of patients from Group 2, who achieve PASI 100 at week 24 and experience relapse	Proportion of patients from Group 2, who not achieve PASI 100 at week 24 and experience relapse
0.00	0.54
0.17	0.77
0.33	0.85
0.50	1.00

With the previous assumptions, the allocation ratio of subjects who achieve PASI 100 in Groups 1 and 2 will be 8:6. On that case a Fisher exact test to compare the proportion of patients who experience relapse with power equal to 0.80 and 95% of significance level will be able to detect significant differences only if the following relationship between proportions is observed:

Proportion of patients from Group 1 who achieve PASI 100 at week 24 and experience relapse	Proportion of patients from Group 2 who achieve PASI 100 at week 24 and experience relapse
0.00	0.67
0.13	0.83
0.25	1.00

3. Power Analysis for Exploratory Objective/Second outcome

To compare the time to relapse between groups with a sample size of 19:19 a Wilcoxon-Mann-Whitney test for nonrelated samples with power equal to 0.8 and 95% of significance level will be able to detect differences only if the effect size observed is equal or larger than 0.96

12.12 * Will samples be coded?

Yes No

If Yes, Please describe coding scheme consistent with GCP. If samples will not be coded, please provide justification for this proposed departure from GCP practice.

Samples will be coded using GCP with the following sequence

NSK__-001. NSK__-002, etc.

If available, upload the Data and Sample Sharing Management Plan approved by RU IT.

Version	Title	Category	Expiration Date	Document Outcome	Checked Out	View Document
No Document(s) have been attached to this form.						

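### Section 12.11 item 2 labels its 12 pairs of relapse proportions as having 80% power, but they are Fisher significance thresholds; exact power is 0.58 to 0.69 in 11 of the 12 rows

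*Combined protocol and SAP*

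**What the plan says.** Section 12.10 fixes the test: "For the comparison between proportions a Fisher exact test will be performed in any case". Section 12.11, item 2, then covers the relapse-frequency comparisons. It assumes that 0.4 of patients reach PASI 100 at week 24 and 0.3 at week 12, applies these rates to 19 patients per group, and obtains three splits:

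- cleared vs not cleared, "for Group 1 (6 month of Secukinumab) will be 8:11";
- cleared vs not cleared, "for Group 1 (6 month of Secukinumab) will be 6:13", although the table beneath is headed "Proportion of patients from Group 2, who achieve PASI 100 at week 24 and experience relapse";
- cleared in Group 1 vs cleared in Group 2: "the allocation ratio of subjects who achieve PASI 100 in Groups 1 and 2 will be 8:6".

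Each split is followed by the same sentence, claiming "power equal to 0.80 and 95% of significance level will be able to detect significant differences only if the following relationship between proportions" in the table is observed. The tables hold five, four and three pairs, 12 in all. Item 2 does not say whether the test is one- or two-sided; a one-tailed test is named only in item 1, for the primary endpoint.

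The aims these tables serve (Section 12.6, Aims 3 and 4) define clearance by IGA, not PASI 100. Aim 4 reads: "To compare frequency of relapse between subjects who achieve a score of 0 (clear) on IGA between group 1 and group 2".

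**The concern.** Every printed proportion is a whole-number count over its group size: 0.45 is 5/11, 0.73 is 8/11, 0.54 is 7/13, 0.83 is 5/6. True rates solved for 80% power would not all fall on such fractions, but the smallest observed counts reaching significance would. A significance boundary and a difference detectable with 80% power are different quantities. When the true rates sit at the boundary, the observed result often falls on the wrong side of it.

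Item 2 is the plan's only power statement for the relapse-frequency comparisons in Aims 3 and 4; item 3 deals with time to relapse. A reader who takes 0.80 at face value will give a non-significant comparison more weight as evidence of no difference than it can bear.

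**Working it through.** **Inputs.** Group sizes 8:11, 6:13 and 8:6 and the 12 pairs come from Section 12.11, item 2. The test is Fisher's exact test (Section 12.10). The stated 95% significance level is read as alpha = 0.05.

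**Step 1: reproduce the printed pairs.** Convert each pair to counts. Compute the two-sided Fisher p at those counts and with one relapse fewer in the second group. For the first row (0.00 vs 0.45, or 0/8 vs 5/11), conditioning on 5 relapses among 19:

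- p = [C(11,5) + C(8,5)] / C(19,5) = (462 + 56) / 11628 = 0.0445
- one fewer, 0/8 vs 4/11: p = [C(11,4) + C(8,4)] / C(19,4) = (330 + 70) / 3876 = 0.103

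All 12 rows behave this way: p is 0.0097 to 0.046 as printed and 0.055 to 0.129 with one relapse fewer. The tables are therefore the two-sided 0.05 significance thresholds. A one-sided 0.05 rule does not reproduce them: it would need only 7/11 against 1/8 and 9/13 against 1/6, where the plan prints 8/11 and 10/13.

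**Step 2: power at the printed pairs.** With true rates p1 and p2,

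power = sum over all (a, b) with Fisher p ≤ 0.05 of Bin(a; n1, p1) × Bin(b; n2, p2).

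Some rows reduce to a single binomial tail and can be checked by hand:

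- 8:11, 0.00 vs 0.45: the first count is always 0, so power = P(Bin(11, 0.45) ≥ 5) = 0.603.
- 8:11, 0.50 vs 1.00: the second count is always 11, and the result is significant if the first is at most 4, so power = P(Bin(8, 0.5) ≤ 4) = 163/256 = 0.637.
- 6:13, 0.50 vs 1.00: P(Bin(6, 0.5) ≤ 3) = 42/64 = 0.656.
- 8:6, 0.25 vs 1.00: the second count is always 6, and 3/8 vs 6/6 is still significant, so power = P(Bin(8, 0.25) ≤ 3) = 0.886.

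**Step 3: all rows, with the second proportion that does give 80% power** (first proportion as printed):

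| Split | Printed pair | Exact power | Second proportion for power 0.80 |
|---|---|---|---|
| 8:11 | 0.00 vs 0.45 | 0.60 | 0.54 |
| 8:11 | 0.13 vs 0.73 | 0.67 | 0.80 |
| 8:11 | 0.25 vs 0.82 | 0.64 | 0.89 |
| 8:11 | 0.38 vs 0.91 | 0.63 | 0.98 |
| 8:11 | 0.50 vs 1.00 | 0.64 | unattainable (maximum 0.64) |
| 6:13 | 0.00 vs 0.54 | 0.62 | 0.61 |
| 6:13 | 0.17 vs 0.77 | 0.67 | 0.83 |
| 6:13 | 0.33 vs 0.85 | 0.58 | 0.96 |
| 6:13 | 0.50 vs 1.00 | 0.66 | unattainable (maximum 0.66) |
| 8:6 | 0.00 vs 0.67 | 0.69 | 0.73 |
| 8:6 | 0.13 vs 0.83 | 0.68 | 0.89 |
| 8:6 | 0.25 vs 1.00 | 0.89 | 0.97 |

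Eleven rows lie at 0.58 to 0.69, that is 0.80 − 0.69 = 0.11 to 0.80 − 0.58 = 0.22 below the claim.

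**Step 4: sensitivity.** With unrounded fractions (1/8 for 0.13, and so on) the 11 rows span 0.57 to 0.70. With a one-sided 0.05 test they span 0.60 to 0.75. The twelfth row stays at 0.89 in both. A normal approximation gives 0.615 to 0.930 two-sided and 0.734 to 0.979 one-sided over the 12 rows. Isolated rows come near 0.80, but no method returns 0.80 throughout.

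**Step 5: related points on the same tables.**

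- *Omitted threshold.* The 8:6 table leaves out 3/8 vs 6/6 (0.38 vs 1.00): p = (56 + 6) / 2002 = 0.031, with power 0.65 at the exact fraction (0.64 at 0.38).
- *Clearance definition.* The only IGA 0 rate given for the drug is 0.24 at week 12 (item 1). Assuming it applies to Group 2 after its three months of drug, 0.24 × 19 = 4.6, a split of about 5:14 rather than 6:13. The thresholds are then 0.00 vs 0.57, 0.20 vs 0.79 and 0.40 vs 0.93 (p = 0.0445, 0.038 and 0.037), with power 0.61, 0.62 and 0.59 at the exact fractions. No week 24 IGA 0 rate is given, so the Group 1 split cannot be rebuilt.
- *Group label.* The 8:6 comparison takes its 6 from Group 2, so the 6:13 split belongs to Group 2, as its table says and its introductory sentence does not.

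**The case against.** The best defence is that the tables answer a different question correctly. The introductory sentences speak of proportions that are observed, item 3 uses similar wording, and as observed-data thresholds all 12 pairs are right. On that view the defect is one misplaced phrase repeated three times, and the shortfall of 11 to 22 points appears only when a threshold is read as an assumed true rate. This stands as a description of how the tables arose. It does not save the statement: power is defined at assumed true rates, the item is headed as a power analysis, and its wording ties 0.80 to the listed pairs.

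A second objection is that the recomputed powers hold only if exactly 8:11, 6:13 or 8:6 occurs, whereas the number of patients who clear is random. This is fair, and any corrected table should say so, although the plan conditions on the splits in the same way. Averaging over a binomial split of 19 does not bring the claim back: it gives 0.46 to 0.67 across the first table and 0.51 to 0.62 across the second.

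Third, item 2 does not state sidedness. One-sided testing narrows the shortfall to 5 to 20 points but does not remove it, and the printed rows fit only a two-sided test.

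Finally, the comparisons are exploratory, and no planned test or decision rule changes. That limits the weight of the point. The clearance-definition and group-label discrepancies are separate consistency matters and add nothing to the power error.

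**Conclusion.** The concern holds. The 12 pairs are two-sided 0.05 Fisher thresholds and the 0.80 power attached to them is wrong. At the printed proportions and splits, exact power is 0.58 to 0.69 in 11 rows, so the probability of missing a true difference of that size is 31% to 42% rather than 20%. One row, 0.25 vs 1.00 at 8:6, has power 0.89, above the claim. In the two rows ending in 1.00 at 8:11 and 6:13 the second rate is already at its ceiling, so 80% power is impossible.

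This rests on alpha = 0.05 two-sided and on the splits occurring as assumed; the one-sided and unrounded variants leave the conclusion unchanged. The consequence is confined to how the exploratory relapse comparisons are read. The correction should be made, but it does not touch the primary analysis.

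**What to change.** Choose one of two corrections to Section 12.11, item 2, and state in either case that the test is two-sided and that the figures apply if the assumed split occurs.

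1. Remove the 80% power claim. Relabel each table as giving, for the stated first proportion, the smallest observed second proportion that reaches two-sided p < 0.05. Add a third column with each row's exact power, and add the missing 8:6 row, 0.38 vs 1.00.
2. Keep the 80% claim. Replace the second column with the 80%-power values tabulated above, and mark the 0.50 rows at 8:11 and 6:13 as unattainable.

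Separately, use one definition of clearance, PASI 100 or IGA 0, in both Section 12.6 (Aims 3 and 4) and these tables. If IGA 0 is kept, state the week 24 rate assumed for Group 1 and rebuild the splits. Change Group 1 (six months) to Group 2 in the sentence that introduces the 6:13 split.

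The cost is wording and table entries. No patients, visits or sample-size change are involved, and Section 17.1 records that recruitment is closed. Under the second option the stated detectable difference becomes larger or unattainable in 11 rows and slightly smaller in one (0.97 instead of 1.00 against 0.25 at 8:6).

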13.0 Participants of Study

13.1 Specify age range of participants:

* Minimum Age:

18

* Maximum Age:

99

Please note: If the age of participants indicated is less than 18 years old, you will be prompted to attach a Pediatric Assent form later on in the submission process. A link to the Pediatric Assent form can be found in the Help link to the right, or this form can be downloaded later on in the submission process.

13.2 * Indicate the gender(s) of the participants:

- Female
- Male
- Unknown
- Not Reported

13.3 * Indicate projected enrollment by race and ethnicity. See Help for disease/volunteer population demographics.

Ethnic Category	Sex/Gender			Total
	Females	Males	Unknown or Not Reported	
Hispanic or Latino	6	5	0	11
Not Hispanic or Latino	12	17	0	29
Unknown				

(individuals not reporting ethnicity)	0	0	0	0
Ethnic Category: Total of All Subjects*	18	22	0	40
Racial Categories				
American Indian/Alaska Native	0	0	0	0
Asian	2	3	0	5
Native Hawaiian or Other Pacific Islander	0	0	0	0
Black or African American	6	9	0	15
White	10	10	0	20
More Than One Race	0	0	0	0
Unknown or Not Reported	0	0	0	0
Racial Categories: Total of All Subjects*	18	22	0	40

13.4 * Will participants of a specific racial/ethnic group be excluded from participation?

Yes No

13.5 Gender/Minority Exclusion Justification

All research involving human participants should be designed and conducted to include members of both genders and members of minority groups, unless a rationale and justification is provided. Please provide such justification below:

13.6 Vulnerable Populations

Indicate whether any of the following populations will be included in the study:

- Children
- Pregnant Women
- Cognitively Impaired Persons
- RU Employees
- RU Students
- Other:

If you checked any of the above, give a brief explanation of the need to use these particular individuals:

RU employees and students will be enrolled if they meet eligibility. Special precautions will be used in recruiting employees and students of the Rockefeller University to minimize the possibility of undue influence. Subjects will be reassured that refusal to participate in the study will not affect their studies or employment in any way and that all medical records will be kept in accordance with HIPAA guidelines to ensure privacy.

If the participant is a Rockefeller University employee, does she/he work within the Laboratory of the Principal Investigator or Co-Investigator(s)?

- Yes
- No
- N/A

If the participant is a Rockefeller University student, does she/he work within the Laboratory of the Principal Investigator or Co-Investigator(s)?

- Yes
- No
- N/A

13.7 *What is the total number of evaluable participants you plan to enroll at Rockefeller University Hospital over the course of the entire study?

40

13.8 * What is the total number of participants who will need to sign consent at Rockefeller University Hospital over the course of the entire study to result in the desired number of evaluable participants?

60

13.9 * What is the total number of participants you plan to sign consent at Rockefeller University Hospital in the next year?

0

13.10 * What will be the total number of evaluable participants at all sites over the course of the entire study?

40

13.11 Inclusion Criteria

Please list participant inclusion criteria:

Order Number	Criteria
1	Written informed consent must be obtained before any assessment is performed
2	18 years of age or older
3	Chronic plaque-type psoriasis for at least 6 months
4	Have a PASI between 6 and 12 and Body Surface Area (BSA) affected by plaque-type psoriasis less than 10% at screening
4	Negative PPD (negative chest w-ray if positive) or negative QuantiFERON-TB Gold.
5	Willing to wash off steroid creams and UVB therapy for 2 weeks prior to the baseline visit

13.12 Exclusion Criteria

Please list participant exclusion criteria:

Order Number	Criteria
1	Has a nonplaque form of psoriasis (eg, erythrodermic, guttate, or pustular)
2	Has previously received Secukinumab or other biologics
3	History of Inflammatory Bowel Disease (IBD)
4	History of Rheumatoid Arthritis
5	Use of topical treatments for psoriasis, including steroids, vitamin D derivatives, vitamin A derivatives, salicylic acid, tar (except moisturizers) and/or UVA/UVB phototherapy within the last 2 weeks (if these have used them, the participant needs to wash off of them for at least 2 weeks after signing consent prior to baseline)
6	Is pregnant, nursing, or planning a pregnancy (both men and women) within 5 months following the last administration of study drug
7	Has recently received or is planning to receive a vaccination while on the study
8	HIV positive
9	Chronic untreated hepatitis C, positive hepatitis B surface antigen
10	Known tuberculosis (TB) or evidence of TB infection. Subjects with a positive QuantiFERON® TB test or a positive purified protein derivate (PPD) skin test result may participate in the study if further work up (according to local practice /guidelines) establishes conclusively that the subject has no evidence of active TB.
11	Any severe, progressive or uncontrolled medical condition at screening that in the judgment of the investigator prevents the subject from participating in the study.

